have obtained a waiver of consent, which was granted warranted because 1) our study is designed to increase uptake of existing screening guidelines; 2) the intervention will not interfere with usual care; and 3) directly recruiting and consenting participants into the RCT might lead to heightened awareness and uptake of CRC screening, which could increase the risk of Type 2 error (failure to detect a beneficial intervention effect) in the RCT. All messages sent to customer-owners will include instructions for opting out of further communications.

There is no compensation provided for the RCT, because no customer-owner will be asked to contribute any time or effort to completing an intervention or engaging in data collection.

Data Collection

All study data will be obtained from the EMR. SCF Data Services staff will extract and de-identify data, and assign unique study IDs to individuals included in the dataset. De-identified data will be securely transmitted to [name] at Washington State University for analysis. The dataset will be stored on a HIPPA-compliant secure server that is backed up daily to an off-side location. Files at Washington State University will be password protected and accessible only to [name]. A member of the study team who also works in the SCF Data Services will retain a second copy of the de-identified study dataset on a password-protected, secure network server at SCF. **Table 1** lists the variables that will be extracted from the EMR.

Table 1. Measures to be extracted from the electronic medical record for the RCT

Variable	Categories or Units	Intended use
Age	40-45; 46-49; 50-59; 60-75	Eligibility, cohort description, subgroup analyses
Gender	Men only	Eligibility
Race	ANAI only	Eligibility
Screening history	Only people without previous abnormal CRC screening results	Eligibility
CRC history	Only people with no previous CRC diagnosis	Eligibility
Location	Urban/suburban; rural	Cohort description, subgroup analyses
Previous CRC screening history	Never screened at SCF; previously screened by colonoscopy; previously screened by other method	Cohort description, subgroup analyses
Duration of overdue screening eligibility	Years (to 1 decimal place)	Cohort description, subgroup analyses
Total SCF clinic visits in the past year	Count	Cohort description, subgroup analyses
CRC screening completed	Type of test Month in which test occurs	Primary outcome
CRC screening or pre-screening scheduled	Yes, No	Primary outcome

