CRC = colorectal cancer; SCF = Southcentral Foundation

D. Statistical analysis

All data analysis will be conducted with Stata version 16 or later (StataCorp, College Station, TX) or R statistical software packages. We will report descriptive statistics for all study variables as counts and frequencies for categorical factors, and as means, standard deviations, and ranges for continuous factors. Descriptive results will be presented separately for men in the intervention and control conditions. Our inferential analysis will use an intent-to-treat approach, using data for all participants in the group to which they were assigned, regardless of events that occur after randomization. We will use logistic regression with marginal standardization to estimate the effect of the intervention on CRC screening. Results will be presented as risk ratios and risk differences with 95% confidence intervals. Marginal standardization estimates are

interpreted as the difference in CRC screening if everyone received the intervention compared to screening if no one received the intervention, in a population with the same distribution of regression model covariates as observed in the study sample. If deemed appropriate, the regression model specification may be adjusted (e.g., binomial regression) prior to conducting the statistical analysis. Our primary analysis will estimate the effect of assignment to the intervention group without adjusting for any covariates, as appropriate for a large RCT. Sensitivity analyses will adjust for any other variables that appear unbalanced between groups at baseline, and secondary analyses will evaluate potential modification of intervention effectiveness by variables such as age, location, and history of CRC screening.

E. Plan for Dissemination

Results from this study will be submitted for publication in the peer-reviewed literature and/or for presentation at scientific conferences. We will also seek out opportunities to share results with SCF and Tribal leadership, customer-owners, and other stakeholders. Documents containing study results (e.g., manuscripts, presentations) will not be made available to the public unless they have first been reviewed and approved by SCF Tribal Review.

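### Section D leaves the primary analysis unadjusted and ties the only main-effect adjustment to undefined baseline imbalance, instead of a fixed set of covariates likely to predict screening

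*Combined protocol and SAP*

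**What the plan says.** Section D names the estimator, "We will use logistic regression with marginal standardization to estimate the effect of the intervention on CRC screening", and the reporting scale, "Results will be presented as risk ratios and risk differences with 95% confidence intervals". It then fixes the primary model: "Our primary analysis will estimate the effect of assignment to the intervention group without adjusting for any covariates, as appropriate for a large RCT". Adjustment of the main effect appears only in the next sentence: "Sensitivity analyses will adjust for any other variables that appear unbalanced between groups at baseline". Section D does not say what counts as unbalanced, which groups are compared, or which variables are candidates.

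Table 1 (Data Collection) already lists three baseline variables that could plausibly predict screening: previous screening history, in three levels ("Never screened at SCF; previously screened by colonoscopy; previously screened by other method"), years overdue, and "Total SCF clinic visits in the past year". Their listed use is description and subgroup work. Section D also names screening history as a possible effect modifier. Section C.2 stratifies randomization on age and location only, so balance on the other three is left to chance.

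**The concern.** After randomization, baseline differences between arms arise by chance. How large a difference looks says nothing about whether the variable predicts screening. The rule can therefore bring in an irrelevant variable and leave out a strong predictor. Because no threshold is set, two analysts could follow Section D faithfully and report different adjusted models.

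The reason given for not adjusting is the size of the trial. Size does not bear on the matter: the proportional reduction in the standard error from a prognostic covariate is much the same at any large sample size. Section D has also chosen a method whose purpose is to use covariates while still estimating a marginal risk ratio and risk difference. With no covariates it simply returns the crude arm proportions.

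At stake are some width in the confidence intervals and the reproducibility of the adjusted result.

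**Working it through.** **Inputs from the documents.** 1000 men, 250 in each of four arms (4 × 250 = 1000, which agrees); stratification on age and location; no covariates in the primary model. The documents state no power, control rate, target effect or R², so there is no design calculation to reproduce. Everything on prognostic strength below is an assumption.

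**Step 1: how often the imbalance rule fires.** For one variable, the standard error of a standardized difference is √(1/n₁ + 1/n₂): √(2/250) = 0.0894 for two arms, and √(1/250 + 1/750) = 0.0730 for control against the pooled active arms. The chance of exceeding a cut t is 2[1 − Φ(t/SE)]. The figures for any pair of four arms come from 1,000,000 simulated sets of arm means. For three independent variables the chance of at least one flag is 1 − (1 − q)³.

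| Meaning of unbalanced | One variable (q) | At least one of three |
|---|---|---|
| 5% test | 5% | 1 − 0.95³ = 14.3% |
| Difference > 0.2, 250 v 250 | 2.5% | 7.4% |
| Difference > 0.2, 250 v 750 | 0.6% | 1.8% |
| Difference > 0.2, any pair of arms | 11.3% | 30.3% |
| Difference > 0.1, 250 v 250 | 26.4% | 60.1% |
| Difference > 0.1, 250 v 750 | 17.1% | 43.0% |
| Difference > 0.1, any pair of arms | 67.8% | 96.7% |

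So the chance that the sensitivity analysis adjusts for anything runs from about 2% to 97%, depending on a definition that the plan does not give.

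**Step 2: what adjustment could gain.** As an approximation, the standard error is multiplied by √(1 − R²), an expression that does not contain n: 0.995 at R² = 0.01, 0.975 at 0.05, 0.949 at 0.10 and 0.922 at 0.15.

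A simulation of 4 × 250 men (2,500 trials per row) compared the unadjusted risk difference for one active arm against control with two alternatives: marginal standardization on all three covariates, and adjustment only for covariates flagged by a 5% test across the four arms. It assumed a risk ratio of 1.5, taken only as an illustration from the result in women quoted in Section B. The covariates were independent, and the stratification factors were not modelled.

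| Control risk | R², control / active | SE ratio, all three | SE ratio, imbalance rule |
|---|---|---|---|
| 10% | 0.010 / 0.014 | 0.994 | 1.001 |
| 10% | 0.032 / 0.044 | 0.985 | 0.997 |
| 10% | 0.085 / 0.110 | 0.955 | 0.992 |
| 20% | 0.017 / 0.022 | 0.993 | 0.999 |
| 20% | 0.053 / 0.067 | 0.981 | 0.994 |
| 20% | 0.128 / 0.152 | 0.930 | 0.987 |

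Full adjustment cut the standard error by 0.6% to 7.0%; the 5% imbalance rule cut it by at most 1.3%. The mean unadjusted estimate stayed within 0.0014 of the true risk difference. A separate simulation of 250 v 250 at 15% control risk gave variance reductions of 0%, 4% and 10% at R² of about 1%, 4% and 9%.

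**Step 3: what that means for power.** For one arm against control at risk ratio 1.5 and two-sided 5%, power at a 20% control risk is 73.4% unadjusted, 73.9% at R² = 0.01 and 80.1% at R² = 0.15. At a 10% control risk the figures are 39.3%, 39.7% and 44.9%.

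**Step 4: how strong the predictors must be.** If half the men were ever screened and their risk differed by 12 points from the rest at an average risk of 15% (all assumed), that variable alone gives R² = 0.06²/(0.15 × 0.85) = 0.0036/0.1275 = 2.8%. An R² near 9% would take about three independent predictors of that strength.

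**The case against.** The strongest reply is that a pre-specified unadjusted intention-to-treat comparison is valid and that this is a preference about efficiency. The first half stands in full. A reader might infer that a chance imbalance too small to be flagged biases the primary result. It does not: on the assumptions of Step 4, the largest imbalance that a 5% test would miss between two arms is 1.96 × √(0.25 × 2/250) = 8.8 points, which moves the risk difference by 8.8 × 0.12 = 1.05 points. The standard error of √(0.15 × 0.85 × 2/250) = 3.2 points already includes that variation.

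Three further limits also stand.

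- The imbalance rule governs sensitivity analyses only. A reader might blame it for lost precision in the main result, but that loss comes from the unadjusted primary model. Rewriting the rule alone narrows no primary interval.
- A reader might infer that the rule usually adjusts for nothing. That holds with a 5% test (0.95³ = 86%) but reverses at a difference above 0.1 between two arms or across all pairs.
- A reader might infer that imbalance among Messages, Gift Card and Raffle would go unseen, because "Descriptive results will be presented separately for men in the intervention and control conditions". Section D does not tie the judgement of imbalance to that table, and Section C.1 calls all four arms conditions, so the table may have four columns.

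It can also be said that screening history already enters a model as an effect modifier. That is a different question and does not adjust the main effect. None of these replies shows that a fixed covariate set would be wrong or costly.

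**Conclusion.** The point holds as one of efficiency and pre-specification. The reproducibility defect needs no assumption about prognosis: Section D selects covariates by an undefined look at chance imbalance, and the resulting model can differ between analysts. The precision gain is conditional. Over an assumed R² of about 1% to 15% it is about 1% to 7% of the standard error, and it is nothing if the covariates do not predict screening.

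A reader might carry away the top of the range, a 10% cut in variance, equal to 1000/0.90 − 1000 = 111 extra men. The documents do not support treating that as the expected gain, because they report nothing on how strongly these variables predict screening. The change is worth making because it costs almost nothing and uses a method already in the plan.

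**What to change.** In Section D, delete the large-trial justification and the imbalance-triggered adjustment. Name one covariate set before outcome data are opened:

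- age and location, as used in the randomization strata;
- previous CRC screening history (three levels);
- SCF visits in the year before randomization;
- years overdue at randomization.

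State the functional form of the visit count and of years overdue. Fit the set in the logistic model with marginal standardization for both primary outcomes, report risk ratios and risk differences with robust or bootstrap 95% intervals, and keep the crude estimates as the supporting analysis.

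If the sponsor keeps an unadjusted primary, this model should replace the imbalance-triggered sensitivity analysis. That removes the data-driven choice but does not narrow the primary intervals.

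The cost is a few sentences in Section D and two anchor dates in the extraction specification, since Table 1 does not date the visit window or the overdue time. Table 1 groups location differently from the strata in Section C.2, so the location stratum should be carried over from the randomization list. No new data collection from participants is needed.
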